### 1483 **7.1.3 Secondary Outcomes at 12 Months (On-Treatment)**

1484 Each secondary analysis below will be conducted using the same approaches as defined above  
1485 for the primary analysis unless otherwise specified.

1486

#### 1487 **7.1.3.1 Refractive Error at 12 Months**

1488 The model used for the primary analysis at 24 months will also be used to perform a treatment  
1489 group comparison of change from baseline to 12-months in spherical equivalent refractive error  
1490 (SER), as measured by a masked examiner using cycloplegic autorefraction.

1491

#### 1492 **7.1.3.2 Proportion of Participants with Progression $\geq 1D$ at 12 Months**

1493 The relative risk of progression of myopia SER  $\geq 1D$  from baseline between participants in the  
1494 atropine group and the placebo group will be estimated using a Cox proportional hazards model,  
1495 adjusting for baseline SER, age, iris color (brown vs. non-brown) and East Asian vs. non-East  
1496 Asian race. An alternative analysis method will be used if the proportional hazards assumption is  
1497 not met.

1498

### 1499 **7.2 Secondary Objective: Efficacy off Atropine Treatment (30 Months)**

1500 The secondary objective of the study is to determine the efficacy of atropine treatment for  
1501 slowing progression of myopia after a period of 6 months off treatment. All analyses as  
1502 described in section 7.1 above will be repeated using data from the 30-month off-treatment visit.

1503  
1504  
1505  
1506  
1507  
1508  
1509  
1510  
1511  
1512  
1513  
1514  
1515  
1516  
1517  
1518  
1519  
1520  
1521  
1522  
1523  
1524  
1525  
1526  
1527  
1528  
1529  
1530  
1531  
1532  
1533  
1534  
1535  
1536  
1537  
1538  
1539  
1540  
1541  
1542  
1543  
1544  
1545  
1546  
1547  
1548

## **7.3 Additional Analyses**

### **7.3.1 Treatment Effect in Subgroups**

The treatment difference for spherical equivalent refractive error (SER) change from baseline to 24 and 30 months within the following subgroups will be explored:

- Baseline SER
- Brown iris versus non-brown iris
- Race/ethnicity
- Baseline age
- Baseline age and baseline SER

These planned subgroup analyses will repeat the primary analysis, including the baseline factor and the baseline factor by treatment interaction. In general, statistical power will be low for detection of interactions unless the interaction is very large.

Subgroup analyses will be interpreted with caution, particularly if the corresponding overall analysis does not demonstrate a significant treatment group difference.

### **7.3.2 Treatment Effect over Time**

The treatment effect on change in spherical equivalent refractive error (SER) from baseline through the first year will be compared with the treatment effect on change in SER from end of first year through the second year, by constructing the appropriate contrasts in the primary analysis model.

### **7.3.3 Exploratory Analyses of Additional Ocular Biometric Parameters**

As exploratory analyses at 24 and 30 months, change in flat corneal radius, anterior chamber depth, and lens thickness will each be compared between treatment groups at 24 and 30 months using a longitudinal discrete time mixed model which allows for interaction between time and treatment group, and adjusts for the baseline value of the parameter, age, iris color (brown vs. non-brown), and East Asian vs. non-East Asian race.

## **7.4 Safety Analyses**

### **7.4.1 Adverse Effects of Eye Drops**

An eyedrops questionnaire will be administered at randomization and at each follow-up visit except the 30-month visit. The distribution of scores on each survey item will be summarized by treatment group at the time of randomization and at each follow-up exam up until and including the 24-month visit. The average of the item responses at the 24-month visit will be calculated and compared with a t-test for difference in means between treatment groups.

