**Table 2. Side Effects/Safety of Atropine Treatment of Myopia**

Study	Ethnicity / Eye Color	Study Type*	N**	Dose***	Side effects
Yen 1989 	Asian	Pro	32	1% ****	All experienced photophobia. No systemic or ocular complications reported.
Kennedy 2000 	Minnesota --mainly white	Retro	214	1%	Photophobia (40.2%), Blurred vision (10.7%), Ocular allergic reaction (3.7%), Ocular discomfort (3.7%), Headache (2.3%), Bad taste in mouth (2.3%), Dry mouth (1.9%), Dry eyes (1.4%), Psychological problems (0.5%), Dizziness (0.5%)
ATOM1 (Chua 2006) 	Asian	Pro	200	1%	No serious adverse events. Study withdrawals due to allergic or hypersensitivity reaction (4.5%), glare (1.5%), and blurred vision (1%)
ATOM1 recovery (Tong 2009) 	Asian	Pro	158	1%	Small decrease in best-corrected visual acuity from baseline, but $\leq 3$ letters in all participants (occurred in controls as well). No reduction in near visual acuity compared with controls. No lens opacities.
Shih 1999 	Asian	Pro	41 47 49	0.5% 0.25% 0.1%	0.5%: light sensitivity persisting >3 months in 22%, 2 children with intolerable photophobia, 2 children with fear of long-term effects, 1 child with recurrent blepharitis. 0.25%: light sensitivity >4 weeks in 7%. No systemic or ocular complications. 0.1%: No light sensitivity beyond 4 weeks. No systemic or ocular complications.
ATOM2 (Chia 2012) 	Asian	Pro	139 141 75	0.5% 0.1% 0.01%	0.5%: Reduced accommodation, impaired near visual acuity, and pupil size increased >3mm. Allergic conjunctivitis (6.2%). Serious adverse reactions (2%) 0.1%: Reduced accommodation, impaired near visual acuity, and pupil size increased >3mm. Allergic conjunctivitis (4.5%). Serious adverse reactions (2%) 0.01%: Serious adverse reactions (1%). Minimally reduced accommodation. No allergic conjunctivitis or dermatitis.
ATOM2 recovery (Chia 2014) 	Asian	Pro	138 139 71	0.5% 0.1% 0.01%	0.5%: Accommodation reduced for 1 year after stopping (2 years administration). Near acuity reduced for an additional month. 0.1%: No effects after stopping 0.01%: No effects after stopping. 7% were given glasses for blur or photosensitivity 
Wu 2011 	Asian	Retro	97	0.05% for 6 months, then 0.1%	No reports of cataract or retinopathy noted during study period. Complaints of near blurring were “uncommon”

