Cooper 2013 	Brown iris U.S. race not specified	Pro	3 6 3	0.05% 0.025% 0.012%	0.05%: Accommodation deficits- no accommodation in 1 participant, 6D accommodation in 2 participants. 0.025%: borderline accommodation in 2 of 6 participants, clinically significant pupil dilation in 4 of 6 participants and minimal in 2 of 6. 0.0125%: 2 of 3 with subnormal accommodation (but no blurred vision).
Lee 2006 	Asian	Retro	21	0.05%	33% had morning photophobia (1 into afternoon). 10% had hampered near vision. No irritation or allergic effects.
Fang 2010 	Asian	Retro	24	0.025%	16% complained of photophobia with atropine vs 8% in control (p=0.4). No complaints of blurred vision. No systemic side effects.
Ekdawi 2015 (AAPOS Poster 2015)	Mostly Caucasian	Retro	7	0.01%	1(14%) participant had headaches and discontinued treatment after 7 months. Participants (number not specified) had difficulty with reading in the first weeks that did not persist past 4-6 weeks with continued use.

\*Study type: Pro = prospective study Retro = retrospective study

\*\*N = number with outcome data.

\*\*\*Treatment is daily unless otherwise noted

\*\*\*\*Treatment is every other day.

615 **1.8 Why is Another RCT Needed?**

616 To date, randomized trials of atropine for slowing the progression of myopia in children have  
617 been primarily conducted on Asian populations. A meta-analysis comparing the effect of  
618 atropine on myopia progression in Asian and White children using data from both RCTs and  
619 prospective cohort studies concluded that atropine may have a greater effect in Asian  
620 populations. A potential explanation of the observed differences of myopia progression  
621 between Asian and White children may be the mydriatic differences observed between highly  
622 pigmented and lowly pigmented eyes in response to atropine. Although results of current  
623 RCTs are promising, additional studies in non-Asian populations are needed to test the efficacy  
624 of atropine in counteracting myopia progression, including dose studies.

625  
626 **1.9 Public Health Importance**

627 The increasing prevalence of myopia and the unresolved problem of myopia progression pose  
628 significant healthcare concerns. Increasing axial length and especially high levels of myopia (>-  

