1172 • Cycloplegic Autorefraction – (see section 2.4)  
1173 • Cycloplegic Axial Length Measurement and Additional Biometry (see section 2.4)  
1174

1175 If a virtual visit is completed, only items 1 through 3 above will be completed. If any safety events  
1176 are identified during a virtual visit, participants will have additional follow up as applicable.  
1177

1178 In addition, females who have experienced menarche will undergo a urine pregnancy test at each  
1179 follow up visit except the 30-month visit (or at home if a virtual visit is completed).  
1180

- 1181 • In the case of pregnancy during the study, study eyedrops will be discontinued although  
1182 the subject will be retained in the study.  
1183

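### The eye drop questionnaire is tested between groups only at 24 months, by a t-test that leaves out the randomization score; the test is valid but needlessly imprecise, and the 6-, 12- and 18-month scores are only described

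*Protocol*

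**What the plan says.** Section 7.4.1 sets the schedule: "An eyedrops questionnaire will be administered at randomization and at each follow-up visit except the 30-month visit". That gives one score before study drops, after the artificial-tear run-in, and four on treatment at 6, 12, 18 and 24 months. Section 4.9 keeps the questionnaire even when the office visit is replaced by a remote one: "If a virtual visit is completed, only items 1 through 3 above will be completed", and the questionnaire is item 3. Section 4.8 allows a virtual visit at 6, 12 and 18 months, but not at 24.

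For analysis, section 7.4.1 first describes all visits: "The distribution of scores on each survey item will be summarized by treatment group at the time of randomization and at each follow-up exam", up to and including 24 months. It then names the single formal comparison: "The average of the item responses at the 24-month visit will be calculated and compared with a t-test". No covariate is mentioned.

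Other continuous outcomes are handled differently. The analyses of refractive error (7.1.1), axial length (7.1.2.2) and the exploratory biometry (7.3.3) each use a longitudinal mixed model with a treatment-by-time interaction and adjustment for the baseline value.

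**The concern.** Two things look wrong. First, the protocol collects a pre-treatment score on every child and then leaves it out of the comparison, although it adjusts for baseline even in its exploratory biometry. Adjusting for a baseline that is correlated with the outcome narrows the interval at no cost in data.

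Second, the only tested time point is the last on-treatment visit. Under section 6.4.2, children who stop study medication continue in follow-up, so some may answer at 24 months while off drops; section 7.8.2 allows for up to 10% loss by then. The safety table in section 1.7 (Table 2) also suggests that symptoms can fade. A small retrospective series at 0.01% reports "difficulty with reading in the first weeks that did not persist past 4-6 weeks with continued use", and a trial reports for its 0.1% arm "No light sensitivity beyond 4 weeks".

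At stake is how a null questionnaire result is read. It could be taken as showing good tolerability throughout, when it would bear only on the 24-month score and with a wider interval than the data allow.

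**Working it through.** **The plan's own figures.** The protocol states no power, standard deviation or correlation for the questionnaire, so there is no questionnaire figure to reproduce. The sample sizes that fix the numbers available do reproduce. With 2:1 allocation the placebo group needs 1.5 × (1.960 + 1.282)² × SD²/Δ².

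- 30 months (SD 0.90 D, Δ 0.50 D): about 51.1, so 52, total 156; 52/0.85 = 61.2, so 62, total 186. This matches section 7.8.3.
- 24 months (SD 0.80 D, Δ 0.50 D): about 40.3, so 41, total 123; 41/0.90 = 45.6, so 46, total 138. This matches section 7.8.2.

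**Inputs for the questionnaire.** 124:62 randomized and 10% loss by 24 months give 124 × 0.9 ≈ 112 and 62 × 0.9 ≈ 56 evaluable. Effects are in SD units of the score. The correlation r is an assumption, shown at 0.3, 0.5 and 0.7.

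**Planned t-test at 24 months.** SE = √(1/112 + 1/56) = 0.1637 SD. The detectable difference is (1.960 + 1.282) × 0.1637 = 0.53 SD at 90% power, and 0.46 SD at 80%.

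**Adding the randomization score.** The variance is multiplied by 1 − r², with r the correlation between the randomization and 24-month scores.

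| r | Variance factor | SE factor | SE reduction | Difference detectable at 90% power |
|---|---|---|---|---|
| 0.3 | 0.91 | 0.954 | 5% | 0.51 SD |
| 0.5 | 0.75 | 0.866 | 13% | 0.46 SD |
| 0.7 | 0.51 | 0.714 | 29% | 0.38 SD |

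Put another way, a difference that the planned test detects with 80% power would be detected with 84%, 90% and 98% power.

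**Averaging the four on-treatment visits.** Under compound symmetry (one correlation r among all five scores) and complete data, the variance factor for the baseline-adjusted mean is (1 + 3r)/4 − r².

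| r | Variance factor | SE factor | SE reduction | Difference detectable at 90% power |
|---|---|---|---|---|
| 0.3 | 0.385 | 0.62 | 38% | 0.33 SD |
| 0.5 | 0.375 | 0.61 | 39% | 0.32 SD |
| 0.7 | 0.285 | 0.53 | 47% | 0.28 SD |

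This second table concerns a different quantity, the average over visits. It is a power gain of that size only if the treatment effect is constant over visits.

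**What a 24-month result says about earlier visits.** Suppose, for illustration, a true difference of 0.5 SD at 6 months. A 6-month t-test with 124:62 and no loss has 89% power. The 24-month t-test with 112:56 has 86% power if the difference persists in full, 33% if it halves, 12% if it falls to a quarter, and 5% (the type I error rate) if it vanishes. The decay patterns are assumed. They show only that no difference at 24 months would not exclude one at 6 months.

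**The case against.** The case for leaving the plan alone is substantial.

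- **The earlier scores are displayed.** Each item is summarized by arm at every visit through 24 months. This stands: a reader might infer that the other scores are discarded, but they are described and merely not compared formally.
- **It is not the only tolerability test.** Section 7.4.2 tests loss of binocular near acuity at 6 months, section 7.5 evaluates the need for bifocals by group, and section 6.1 queries ocular side effects as adverse events. This stands too.
- **The t-test is not biased.** Section 3.5 keeps every randomized child in the analysis whatever treatment is received. With complete data the t-test is unbiased for the 24-month difference between groups as randomized. A reader might infer bias toward no difference, from intolerant children stopping drops and then scoring as symptom-free. The protocol neither shows the questionnaire items nor says how children off drops score, and it does not quantify intolerance-related loss. Leaving out the baseline costs precision, not validity.
- **A 6-month contrast would not reach the symptoms cited.** Symptoms that clear within 4 to 6 weeks are gone before the first on-treatment questionnaire. They rest on the 2-week and 3-month calls (section 4.3) and adverse event recording. The 0.01% report comes from a series of seven. So it is an inference, not a protocol statement, that intolerance is most likely to show early.
- **24 months is a defensible visit.** It follows the full course, coincides with the primary outcome, and is the only on-treatment visit without a virtual option. That is a good reason to keep it as the main contrast.
- **Chapter 7 calls itself a framework for a later analysis plan.** True, and that plan is not at hand. But section 7.4.1 itself names the visit and the test, so the choice has been fixed here.

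What survives is narrower: a collected baseline is not used, and the intermediate visits yield no estimated group difference.

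**Conclusion.** The point holds as one of precision and of scope. The sole questionnaire comparison is valid, but it is less precise than the collected data permit, and it speaks only to 24 months. The firm figure is a 5 to 29% smaller standard error at 24 months from baseline adjustment alone, for an assumed correlation of 0.3 to 0.7 between the randomization and 24-month scores. A lower correlation would give less.

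The 38 to 47% reduction should not be quoted as the gain of the fix. It belongs to the four-visit average, rests on compound symmetry and complete data, and becomes power only if the effect does not change over visits, which sits badly with an argument that symptoms fade. No stated number in the protocol is wrong, and no primary or secondary efficacy conclusion is affected.

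**What to change.** Reword section 7.4.1, and carry the change into the analysis plan, along these lines:

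- Analyse the mean item score at 6, 12, 18 and 24 months in the same type of longitudinal mixed model as the primary outcome, with a treatment-by-visit interaction and adjustment for the randomization score.
- Keep the 24-month treatment difference as the one prespecified contrast.
- Report the 6-month difference and the average over the on-treatment visits with confidence intervals, labelled as supporting estimates. This avoids a multiplicity problem: four separate unadjusted tests at 5% would carry a familywise error of 1 − 0.95⁴ = 18.5% if independent.
- Keep the item-by-item summaries by arm.
- State that symptoms resolving within the first 4 to 6 weeks are not captured by any scheduled on-treatment questionnaire and are assessed through the 2-week and 3-month calls and adverse event recording.

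The cost is slightly more analysis work. No new data, visits or forms are needed.

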### **7.4.2 Visual Acuity**

The proportion of participants with loss of best corrected distance vision >1 logMAR line at 30 months in either eye will be compared between treatment groups using Barnard's test. The proportion of participants with loss of best corrected near binocular vision >1 logMAR line at 6 months will be compared between treatment groups using Barnard's test.

1549 **7.5 Need for Bifocals**

1550 The proportion of participants needing bifocals in both groups will be evaluated.

1551

1552 **7.6 Interim Analysis**

1553 As specified by the DSMC, the decision of whether an interim analysis will be conducted will be  
1554 evaluated after 6 months of recruitment and before any outcome data is reviewed. An interim  
1555 monitoring plan will be developed at that point if circumstances warrant.

1556

1557 **7.7 Data Tabulations and Other Analyses**

1558 The following tabulations will be performed according to treatment group:

- 1559 • Baseline demographics and clinical characteristics
- 1560 • A flow chart accounting for all participants for all visits and phone calls
- 1561 • Visit and phone contact completion rates for each follow-up visit
- 1562 • Protocol deviations

1563

1564 **7.8 Sample Size**

1565 **7.8.1 General Considerations**

1566 The goal of this section is to summarize data from prior studies of myopia progression, use these  
1567 data to formulate assumptions about the expected treatment effect and its standard deviation, and  
1568 to calculate the sample size needed to provide at least 90% power for each of the 2 hypothesis  
1569 tests corresponding to the 24-month on treatment (primary) and 30-month off-treatment  
1570 secondary objectives.

1571

1572 To collect more safety data from participants using atropine, sample size was based on a 2:1  
1573 allocation (2 participants will be randomized to the atropine group for every 1 participant  
1574 randomized to the placebo group).

1575

1576 **7.8.2 Sample Size for Primary Objective: Efficacy on Atropine Treatment**

1577

1578 **Comparison of SER at 24 months**

1579 Sample size calculations for the on-treatment comparison of refractive error at 24 months were  
1580 based upon data from the CLEERE group and ATOM1 for untreated participants meeting similar  
1581 eligibility criteria, and data from participants treated with atropine 0.01% in the ATOM2 study.  
1582  The participants in these studies were 6 to <13 years old with refractive error of -1.00D to -  
1583 6.00D spherical equivalent and astigmatism of -1.50D or less. The ATOM1 and ATOM2 studies  
1584 were conducted in Asian populations whereas the race/ethnicity of participants in the CLEERE  
1585 study was more reflective of the US population.

1586

- 1587 • In 404 untreated participants from CLEERE (N=214) and ATOM1 (N=190), the mean  
1588 progression after 24 months was 1.12D (95% CI = 1.05 to 1.18D) with standard deviation  
1589 (SD) of 0.69D (95% CI = 0.65 to 0.75D).

1590

- 1591 • In 75 participants treated with 0.01% atropine from ATOM2, the mean progression after  
1592 24 months was 0.49D (95% CI = 0.35 to 0.63D) with SD of 0.60D (95% CI = 0.52 to  
1593 0.72).

1594

1595 The on-treatment effect after 24 months in our study is estimated to be 0.50D based on a  
 1596 conservative estimate of 1.00D 24-month progression in untreated participants and an estimated  
 1597 0.50D 24-month progression in participants treated with 0.01% atropine.

1598  
 1599 Assuming a conservative standard deviation of 0.80D (based on CLEERE), and using a 2-sided  
 1600 t-test with alpha = 0.05, a sample size of 123 participants (82 in the atropine group and 41 in the  
 1601 placebo group) is needed to detect a difference in mean change in SER (atropine – placebo) at 24  
 1602 months with 90% power, assuming the true mean difference is 0.50D or larger (Table 1).  
 1603 Since the correlation between baseline refractive error and change in refractive error at 24  
 1604 months in the CLEERE data was low (r=0.05), no reduction in sample size was taken to account  
 1605 for the correlation between baseline and the outcome at 24 or 30 months. Accounting for up to  
 1606 10% loss to follow-up over 24 months, the sample size *for this objective* is 138 participants  
 1607 overall (92 in the atropine group and 46 in the placebo group).  
 1608

1609 **Table 1: Total Sample Size Estimates for Various Treatment Group Differences in Mean**  
 1610 **SER Score at 24 Months or 30 Months\***

Standard Deviation Mean SER Change from Baseline to 24 Months or 30 Months(D)	True Treatment Group Difference (D) in Mean SER Change between Baseline and 24 Months or 30 Months			
	0.40	0.50	0.60	0.625
0.60	111 (74:37)	72 (144:72)	51 (34:17)	48 (32:16)
0.70	147 (98:49)	96 (64:32)	69 (46:23)	63 (42:21)
0.80	192 (128:64)	123 (82:41)	87 (58:29)	81 (54:27)
0.90	243 (162:81)	156 (104:52)	111 (74:37)	102 (68:34)
1.00	300 (200:100)	192 (128:64)	135 (90:45)	123 (82:41)

1611 Cells indicate total sample size needed assuming a 2:1 randomization. (Numbers in parenthesis reflect number  
 1612 needed in each group atropine:placebo).

1613 \*Sample sizes based on a t-test to evaluate a difference between treatment groups in mean change from baseline at  
 1614 24-months, with a 2-sided alpha=0.05, and power=90%.  
 1615

